2.5.4 Safety Analysis

Section 6.4.5 outlines all potential SAE's and defines a SUAE as any SAE that occurs in the setting of $\text{MetHb} > 10\%$ which may thus be attributed to the study drug. All listed safety outcomes will be tabulated and summarized using basic descriptive statistics and tested using small sample exact methods.

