6.4.5 Reportable Adverse Events

This is a high risk population in which numerous serious adverse events are expected. Indeed, all subjects will require mechanical ventilation, with >50% of subjects expected to require >50% FiO₂ and/or vasopressors during the first 24 h based on our prior data^{33,34} and expected mortality is 70-80%³⁵ as we are excluding non-comatose subjects. Thus numerous serious adverse events (SAE) are anticipated during the conduct of this study with a complete list provided below. In this context we define a SUAE as any SAE that occurs in the setting of MetHb > 10% which may thus be attributed to the study drug.

Expected SAE (with severity grade indicated)

- Non-central nervous system thrombosis, particularly in vessels accessed for endovascular devices, assessed as symptomatic venous or arterial thrombus documented radiographically or ultrasonographically. (Grade 3)
- Sepsis assessed as the presence of microbiologically proven, clinically proven, or suspected infection; presence of Systemic Inflammatory Response Syndrome (SIRS); and development of at least one organ dysfunction within the preceding 24 hours. Diagnosis of SIRS will require the fulfillment of at least two of the following criteria (Grade 4):
 - Hyperthermia ($\geq 38^{\circ}\text{C}$) (which will only be evident after active temperature control);
 - Tachycardia ($\geq 90 \text{ bpm}$);
 - Tachypnea ($\geq 20 \text{ breaths/min}$) or an arterial pCO₂ $\leq 4.3 \text{ kPa}$ (32 mmHg) or mechanical ventilation;
 - White blood cell count $\geq 12,000/\mu\text{L}$ or $\leq 4,000/\mu\text{L}$ or left shift in differential white blood cell count $\geq 10\%$.
- Expected organ dysfunctions after OHCA (which may accompany SIRS in sepsis as defined above or separately) will be defined as:
 - Acute encephalopathy not explained by psychotropic medication (or attributable to the cardiac arrest) [Grade 3];
 - Thrombocytopenia $\leq 100,000/\mu\text{L}$ or drop in platelet count $> 30\%$ within 24 hours not explained by hemorrhage (Grade 3);
 - Arterial hypoxemia with an arterial pO₂ $< 8 \text{ kPa}$ (60 mmHg) when breathing room air or an oxygenation index (paO₂/FiO₂ $\leq 200 \text{ mmHg}$) not explained by presence of a pulmonary or cardiac disease (Grade 4);

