 - Arterial hypotension with a systolic blood pressure $\leq 90 \text{ mmHg}$ or mean arterial blood pressure $\leq 65 \text{ mmHg}$ for at least one hour despite adequate fluid loading not explained by other causes of shock (Grade 4);

- Renal dysfunction with urine output ≤ 0.5 mL/kg/h for at least one hour despite adequate fluid loading or serum creatinine above 200 $\mu\text{mol/L}$ (2.3 mg/dL) [Grade 3];
 - Metabolic acidosis with base deficit ≥ 5.0 mmol/L or serum lactate ≥ 1.5 fold above local reference range (2.4 mmol/L at UPMC) [Grade 3].
- Pneumonitis assessed as the presence of air bronchograms on any chest x-ray within one week of the index cardiac arrest. (Grade 3)
- Since many of these comatose OHCA subjects will receive therapeutic hypothermia, anticipated SAE include:
 - Electrolyte abnormalities: defined as the presence of any of the following from induction of hypothermia until 72 hours (all Grade 3):
 - Hypokalemia assessed as serum potassium concentration < 3.5 mmol/L.
 - Hyperglycemia assessed as serum glucose > 240 mg/dL.
 - Hypophosphatemia assessed as serum phosphate concentration < 0.8 mmol/L.
 - Hypocalcemia assessed as serum ionized calcium < 2.2 mmol/L.
 - Bleeding (overt bleeding with Hb drop > 3 g/dL or transfusion; cardiac tamponade; bleeding requiring surgical intervention for control or intravenous vasoactive agents; intracranial hemorrhage; intraocular bleed compromising vision; operation for vascular closure for the purpose of controlling bleeding; fatal bleeding) [Grade 3]
 - Thrombosis (Grade 3)
 - Infection (Grade 3)
 - Fluid shifts defined as net fluid intake/output exceeding 3 L positive or negative in a 24h period (Grade 3)
- Pulmonary Edema: We shall monitor the incidence of pulmonary edema in each treatment duration group and assess whether there is a significant difference between groups. It will be defined as the presence of congestive heart failure on a hospital-based chest x-ray (first emergency department or ICU chest x-ray). OHCA is more common in patients with cardiomegaly, and this radiographic sign alone will not be a criterion for diagnosis of acute heart failure. (Grade 3)

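### The hypocalcemia cut-off in 6.4.5 flags practically every ionized calcium result in cooled subjects, so the item and the electrolyte composite that contains it cannot inform on safety

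*Combined protocol and SAP*

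**What the plan says.** Section 6.4.5 (Reportable Adverse Events) sets out a list headed "Expected SAE (with severity grade indicated". One part of it is introduced by "Since many of these comatose OHCA subjects will receive therapeutic hypothermia, anticipated SAE include", and within that part electrolyte abnormalities are "defined as the presence of any of the following from induction of hypothermia until 72 hours (all Grade 3". Four items follow: low potassium, high glucose, low phosphate and "Hypocalcemia assessed as serum ionized calcium < 2.2 mmol/L".

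Section 2.5.4 (Safety Analysis) says what is done with the list: "All listed safety outcomes will be tabulated and summarized using basic descriptive statistics and tested using small sample exact methods".

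No other section gives a calcium range, a second unit or a different cut-off. Neither ionized nor total calcium is named among the data elements in section 2.2 or in Table 1.

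**The concern.** A cut-off of 2.2 mmol/L is on the scale of total calcium, but the analyte named is ionized calcium, which runs at roughly half of total. A subject with an unremarkable ionized value would be recorded with a Grade 3 SAE. A definition that nearly everyone meets cannot separate the arms. Two things are at stake: whether one pre-specified safety comparison has any content, and whether the adverse-event data that the DSMB reviews contain events that reflect a slip in a definition and nothing about the subject.

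**Working it through.** The cut-off has no derivation in the plan, so there is no figure to reproduce. The check asks how often the definition would be met and what follows for the tabulated outcome.

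**1. Are the neighbouring limits consistent in their units?** Three limits in 6.4.5 carry two units.

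- Creatinine: 200 µmol/L ÷ 88.42 = 2.26 mg/dL (stated 2.3).
- pCO2: 4.3 kPa × 7.50062 = 32.3 mmHg (stated 32).
- pO2: 8 kPa × 7.50062 = 60.0 mmHg (stated 60).

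All three agree. The calcium line carries one unit only, so it offers no such internal check.

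**2. The calcium limit in other units.** 2.2 mmol/L × 4.0078 = 8.8 mg/dL. Calcium is divalent, so this is 2.2 × 2 = 4.4 mEq/L. Read the other way, 2.2 mEq/L ÷ 2 = 1.1 mmol/L.

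**3. How often an ionized result falls below 2.2 mmol/L.** Assumption, not in the documents: ionized calcium is roughly normal with mean 0.9 to 1.4 mmol/L and SD 0.05 to 0.3. Then P(X < 2.2) = Φ((2.2 − mean)/SD).

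| Mean | SD 0.1 | SD 0.2 | SD 0.3 |
|---|---|---|---|
| 0.9 | 1.000 | 1.000 | 0.99999 |
| 1.2 | 1.000 | 1.000 | 0.9996 |
| 1.4 | 1.000 | 0.99997 | 0.996 |

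At SD 0.05 every entry is 1.000. The least favourable corner is (2.2 − 1.4)/0.3 = 2.67, which gives 0.996. The mean would have to be far above the assumed range before the definition began to discriminate.

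**4. How many subjects.** The item sits under therapeutic hypothermia, and the plan says only that many subjects will be cooled. Planned N is 130. With an assumed fraction cooled f and fraction of those tested t, the number flagged is about 130 × f × t.

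| Cooled | All tested | Half tested |
|---|---|---|
| 50% | 65 | 33 |
| 75% | 98 | 49 |
| 100% | 130 | 65 |

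These figures illustrate a range and are not estimates. Neither fraction is in the documents.

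**5. What the exact test returns.** Section 2.5.4 does not state the denominator.

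- *Tested subjects only.* Practically all are events in both arms. With no non-events the 2×2 table has an empty column and Fisher's p = 1, whatever the calcium values were.
- *All randomized subjects, untested counted as non-events.* The event becomes having been cooled and having an ionized result. As an illustration with 65 per arm, 30 against 40 flagged gives p = 0.11 and 25 against 40 gives p = 0.014. A small p-value here would reflect cooling and sampling practice.

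Neither denominator yields information about calcium.

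**6. The composite.** Any one of the four items makes the electrolyte outcome positive. A subject with an ionized result is therefore positive whatever the potassium, glucose and phosphate values are, and the composite inherits the problem in step 5.

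**The case against.** The strongest reply concerns reach and consequence, and much of it stands.

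- *Scope.* A reader might infer that all 130 subjects would be flagged. The documents do not support this. The item applies after induction of hypothermia, within 72 hours, and only where an ionized result exists. The figure of 130 is a ceiling that needs every subject to be cooled and tested.
- *The p-value.* A reader might infer that p = 1 is inevitable. It follows only if the denominator is tested subjects, which section 2.5.4 does not say. The other denominator gives a different failure, not a sound test.
- *False events.* A reader might infer one spurious SAE per tested subject. Some will have met the composite through another item, and some may truly have low calcium. The plan also does not say whether the composite or the single items are tabulated. If the items are reported separately, potassium, glucose and phosphate remain readable and only the calcium row is lost.
- *Expedited reporting.* A reader might infer a flood of reports. These are expected SAEs, and the plan's trigger is explicit: "we define a SUAE as any SAE that occurs in the setting of MetHb > 10% which may thus be attributed to the study drug". For a flagged subject the SAE half of that condition is met automatically, but methemoglobin above 10% is still required, and section 2.3.3 already treats that level as a significant and unexpected adverse event.
- *Which element is wrong.* It is tempting to conclude that total calcium was meant. A unit slip fits too (2.2 mEq/L is 1.1 mmol/L), and so does a wrong number. The documents cannot settle it.
- *Clinical common sense.* Staff may notice the problem and apply a limit of their own. That would leave the written rule unused and the scoring unrecorded, which is a reason to correct the text.

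None of this makes the line workable as written.

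**Conclusion.** The point holds in this limited form. As written, the definition is met by practically every cooled subject with an ionized calcium result between induction and 72 hours: 0.996 to 1.000 of results under the assumed distributions. That rests on one assumption from outside the documents, that ionized calcium centres within about 0.9 to 1.4 mmol/L, and the conclusion is insensitive to where in that range it lies. The number of subjects affected is unknown.

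The consequence is a safety outcome that is scheduled for tabulation and testing but carries no information on calcium, and an electrolyte composite that is positive by construction for the same subjects. The primary endpoint and the efficacy analyses are untouched, and the item alone does not trigger expedited reporting. It is a clear error in a definition, modest in consequence, and worth correcting because the correction is so small.

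**What to change.** The sponsor should reconcile three things in the hypocalcemia line of section 6.4.5, and on any form that repeats it: the analyte (ionized or total), the unit (mmol/L or mEq/L) and the cut-off. The same list refers to the local laboratory's reference range for lactate, and a check of the calcium line against that laboratory's range would show which element is out of place. This review does not say which limit is clinically right.

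Two additions would complete the correction. Section 2.5.4 should state whether the electrolyte items are tabulated singly, as the composite, or both, and whether the denominator is all randomized subjects, cooled subjects or tested subjects. Events already recorded under the present line should be re-scored where a calcium value is available. Because calcium is not a scheduled data element, it cannot be assumed that one exists for every subject.

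The cost is one line in 6.4.5, a sentence in 2.5.4, any matching form change, and limited re-scoring. Sample size and the primary analysis do not change.

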2. RESEARCH DESIGN AND METHODS

2.1 CLASSIFICATION AND METHODOLOGICAL DESIGNS

The iNO OHCA study is a phase II double blind (participants and investigator) placebo controlled randomized (1:1) clinical trial of iNO 20 ppm administered over 12h (with 1 h weaning off) beginning as soon as possible but within 4 h of return of spontaneous circulation (ROSC) after OHCA. Planned enrollment is 130 subjects over 24 months at UPMC Presbyterian (PUH) and Mercy (MER) with randomization stratified in blocks of 8. Recruitment will be performed under exception from informed consent (EFIC) to facilitate early enrollment and treatment. The study will have a safety monitor to assess any concerns during its conduct and a pre-specified safety analysis at the mid-point (after 1 year or 60 patients whichever occurs first). Subjects or their surrogate (as subjects will be enrolled when comatose) will be notified as soon as possible by a member of the research team of enrollment and can elect whether to permit blood banking for future genetic studies.

Duration of subject participation is 90 ± 3 d of ROSC. Most data will be collected within four days of ROSC, which includes the 12h of study drug administration and 1h weaning of study drug. After the initial four days have passed follow up will be done at hospital discharge (DC; which includes death), day 30, and day 90 after OHCA to evaluate outcomes.

Subjects will not be withdrawn from or prevented from receiving any known effective therapy for the purposes of participating in this research.

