Eligibility will be determined by a University of Pittsburgh Post-Cardiac Arrest Service (PCAS) physician, all of whom are routinely consulted in the care of this patient population and will serve as co-investigators on the study. Inclusion and exclusion criteria will be based on clinical characteristics (see attached Screening questionnaire). Due to the urgent need for intervention in this population, we will enroll subjects under an exception from informed consent (EFIC). Once eligibility is determined, patients will be randomized using block randomization to receive iNO or placebo. Randomization will be stratified in blocks of 8 by center. The randomization list will be created prior to the beginning of the study by the Respiratory Therapy (RT) directors ([name], PUH, and [name], MER) and confirmed by a representative of Mallinckrodt. These 3 individuals who will not be involved in any portion of the conduct or analysis of the study will retain these lists and update them as additional subjects are enrolled using new canisters of study drug. This list will set an order in which canisters of iNO study drug, coded by bar code, will be administered at each site. Treatment assignment will be made known to the study team after enrollment is confirmed by means of a sealed opaque envelope which contains the cylinder barcode for the subject as well as the subject ID. These envelopes will be with other research materials at each study site. iNO canisters will be stored in PUH Rm A-125 and Mercy (ED compressed gas storage). Prior to each enrollment the next canister to be used at a site will be loaded onto an iNOVent delivery device and the gas calibrated permitting rapid deployment to the next subject enrolled at that site. Check lists will be maintained as each site documenting calibration and each use on a study subject. The gas canister bar code will be recorded in our

database with the subject ID permitting subsequent unblinding of treatment assignment. Canisters will be used for 4 subjects prior to return to the company and replacement with a new (full) canister of study drug.

A clinical respiratory therapist (RT) will administer iNO at 20 ppm for 12h, with a 1h wean consisting of 10 min at 10 ppm, 10 min at 5 ppm, 10 min at 4 ppm, 10 min at 3 ppm, 10 min at 2 ppm, and 10 min at 1 ppm before subject is taken off of study drug. Study drug will generally be connected in the emergency room or ICU.

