5. RECRUITMENT AND INFORMED CONSENT PROCEDURES

5.1 RECRUITMENT METHODS:

PCAS physicians are generally alerted to incoming resuscitated cardiac arrest patients either through a med call page (to accept the patient in transfer) or a page from emergency medical services stating the patient is en route to the emergency room (ER). PCAS physicians will review details of the patient's cardiac arrest to determine eligibility in consultation with a study coordinator. The ultimate designation of whether a patient is eligible will require a physical exam to determine neurologic function and hemodynamic stability upon ER presentation. If a patient is deemed eligible, they will be enrolled into the trial. We are requesting a waiver of informed consent to both review medical records to determine eligibility, and to enroll patients in the trial.

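### The planned arm comparison of pulmonary edema is read on the first ED or ICU chest film, with no requirement that it follow study drug and no baseline, so pre-drug films can dilute it by an unknown amount

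*Combined protocol and SAP*

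**What the plan says.** The pulmonary edema entry in section 6.4.5 announces a comparison: "We shall monitor the incidence of pulmonary edema in each treatment duration group and assess whether there is a significant difference between groups". It then fixes the film on which the event is read: "It will be defined as the presence of congestive heart failure on a hospital-based chest x-ray (first emergency department or ICU chest x-ray". It gives no timing relative to study drug, names no baseline film, and does not say whether the emergency department of a referring hospital counts. Section 2.5.4 adds that listed safety outcomes are tested by exact methods, but no timing rule.

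The sequence of care comes from other sections. Eligibility "will require a physical exam to determine neurologic function and hemodynamic stability upon ER presentation" (section 5.1). Drug starts "beginning as soon as possible but within 4 h of return of spontaneous circulation (ROSC) after OHCA" (section 2.1), and "Study drug will generally be connected in the emergency room or ICU" (section 2.2). Some patients reach the service "either through a med call page (to accept the patient in transfer" (section 5.1), and section 2.3.3 says that most patients at the larger center arrive by transport 1 to 3 hours after ROSC.

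The same list in section 6.4.5 treats another radiographic event differently: "Pneumonitis assessed as the presence of air bronchograms on any chest x-ray within one week of the index cardiac arrest".

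**The concern.** Section 6.1.1 names raised wedge pressure and worsening heart failure as possible effects of inhaled nitric oxide. Pulmonary edema is the listed event closest to that risk, and the only one for which section 6.4.5 itself announces a comparison of the groups. If part of the comparison rests on films taken before any drug was given, it is pulled toward no difference whatever the drug does. A single early film also misses edema that develops later in the 12 hours of drug. A null result would then look reassuring while carrying little information.

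The label for the groups is also out of place. It refers to duration of treatment, but the trial has two arms, nitric oxide and placebo, with one planned duration.

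**Working it through.** **No stated figure to reproduce.** The documents give no edema rate, no power for this comparison and no share of pre-drug films. All rates below are assumptions. The inputs from the plan are 130 subjects randomized 1:1, so 65 per arm (section 2.1); two-sided 0.05 (section 2.5.2); and an exact test (section 2.5.4), taken here as Fisher's. Power is by full enumeration of two binomials.

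**Can a qualifying film precede drug?** Yes. The eligibility exam takes place after arrival in the emergency department, and drug is connected afterwards, there or in the ICU. A film from a referring hospital, if it counts, must precede drug, because drug is given only at the two study sites.

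**Step 1: dilution alone.** Randomization makes pre-drug rates equal in expectation, so expected observed difference = (1 − f) × post-drug difference. Take 20% edema on any pre-drug film and on placebo post-drug films. The observed nitric oxide rate is then 0.20f + (1 − f)p, where p is its post-drug rate.

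| f | Power, p = 40% | Power, p = 30% |
|---|---|---|
| 0 | 64% | 20% |
| 0.25 | 41% | 12% |
| 0.5 | 20% | 7% |
| 0.75 | 7% | 4% |
| 1 | 3% | 3% |

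At f = 1 only the false-positive rate of the exact test remains, and it is below 5%. Type I error is therefore not inflated.

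**Step 2: precision.** With 20% edema in both arms, the 95% half-width on the film difference is 1.96 × √(2 × 0.2 × 0.8 / 65) = 13.8 points. Dividing by (1 − f) puts it on the scale of the post-drug difference: 13.8, 18.3, 27.5 and 55.0 points at f = 0, 0.25, 0.5 and 0.75.

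**Step 3: what a better definition could gain.** Let b = 20% have edema before drug, and let new or worsened edema arise in q = 10% (placebo) against 30% (nitric oxide), independently of baseline. A post-drug film shows edema with probability b + (1 − b)q, which is 28% against 44%. Assume that baseline films exist only in the share f.

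- As written: event rate = f·b + (1 − f)[b + (1 − b)q].
- Under the change proposed below: event rate = f·q + (1 − f)[b + (1 − b)q].

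| f | As written: rates, power | Proposed: rates, power |
|---|---|---|
| 0 | 28% vs 44%, 42% | 28% vs 44%, 42% |
| 0.25 | 26% vs 38%, 25% | 23.5% vs 40.5%, 48% |
| 0.5 | 24% vs 32%, 13% | 19% vs 37%, 56% |
| 0.75 | 22% vs 26%, 6% | 14.5% vs 33.5%, 66% |
| 1 | 20% vs 20%, 3% | 10% vs 30%, 78% |

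The as-written column assumes that the single film catches all new edema, which favors the current rule.

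**Step 4: why subjects without a baseline film must stay in.** If only subjects with a pre-drug and a post-drug film were analyzed, usable numbers would be about 65f per arm. At f = 0.25 that is 16 per arm, and power for 10% vs 30% is 17%, below the 25% of the current rule. At f = 0.5 (33 per arm) it is 42%, below the 56% obtained by keeping everyone.

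**The case against.** Four points weigh on the other side.

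1. **The parenthesis is ambiguous.** It can mean the first emergency department film, or any ICU film. That reading is tenable and makes the dilution smaller. Edema already present before drug would still count in both arms: if the films together catch all new edema, the Step 3 illustration gives 28% vs 44% and 42% power.

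2. **The share f may be low.** The delivery device is loaded in advance, "permitting rapid deployment to the next subject enrolled at that site", and a first ICU film may well follow drug. This stands. A reader might infer that every film precedes drug and that the comparison is empty; the documents do not support that.

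3. **Sample size limits the test anyway.** With 20% against 30% and no pre-drug films, power is only 20%. This stands too, and a small harm would be missed under any definition.

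4. **The risk is watched elsewhere.** Discharge NYHA class is part of the primary composite. Ejection fraction, TAPSE, cardiac output and inotrope need are secondary endpoints (section 2.4). BNP, ventilator settings and respiratory SOFA are collected on days 1 to 3 (section 2.2), and section 6.1.1 has the safety monitor review change on chest films for each patient. A reader might infer that the trial cannot see worsening heart failure; that would be wrong. None of these measures, however, repairs the film comparison itself.

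It is also tempting to set 42% power under the current rule against 78% under a baseline-adjusted rule. That pairing does not hold. The 42% belongs to f = 0, where under the first-film reading nobody has a pre-drug film, and the 78% requires everybody to have one.

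**Conclusion.** The point holds as a dilution of unknown size in one safety comparison, under a definition that can be read two ways. Its direction follows from the design: any pre-drug film carries no treatment effect, and pre-existing edema adds events that drug did not cause. Its size rests on f and on edema rates that the documents do not give, so the powers above are illustrations and not estimates for this trial. The primary analysis is untouched. What suffers is how much a null edema result can say about a risk that the protocol itself names. That warrants a correction, because the remedy is cheap.

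The gain from the remedy depends on f as well. There is none at f = 0 if no baseline film exists. The gain is smaller if worsening cannot be read on an already abnormal film: with only new edema detectable, 10% vs 30% becomes 0.8 × 10% = 8% vs 0.8 × 30% = 24%, and power with all 65 per arm is 64% instead of 78%.

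**What to change.** Reword the pulmonary edema entry in section 6.4.5 as follows:

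- The event is pulmonary edema on any clinically obtained chest film from study drug start through day 3, abstracted blind to arm.
- Where a pre-drug film exists, including one from a referring hospital, only new or worsened edema counts.
- Where none exists, any edema on a post-drug film counts, so that no subject is dropped for lack of a baseline.
- Nitric oxide and placebo are compared by the exact test already planned in section 2.5.4.
- The number without a baseline film and the number without a post-drug film, including early deaths, are reported by arm.
- The group label is replaced by the nitric oxide and placebo groups.

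The cost is protocol wording and one case report form item, since the current chest-film items in section 2.2 record only possible pneumonia. No extra films are needed, because section 6.1.1 describes them as usually taken every day. Three drawbacks remain. Some subjects will have no post-drug film. A window through day 3 will also pick up some edema unrelated to drug. And because section 6.4.7 ends imaging data collection after withdrawal for a serious adverse event, the plan must state whether routine film reports are still abstracted in those subjects.

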3.3 EXCLUSION CRITERIA

Exclusion criteria do not change any subgroups.

- Traumatic etiology of OHCA
- Prisoner
- Known pregnancy
 - o B-HCG screening is NOT REQUIRED for enrollment in women of appropriate age
- Hemodynamic instability defined as:
 - o > 1 recurrent arrest prior to enrollment
 - o Inability to maintain mean arterial blood pressure (MAP) > 65 using vasopressors and inotropes (ie actively up titrating medications or giving fluid bolus)
- Cerebral edema defined as:

- Head CT grey-white ratio < 1.2
 - Fixed and dilated pupils without another explanation
- Malignant EEG upon presentation (not required as screening) defined as:
 - Myoclonic status epilepticus
 - Non-convulsive status epilepticus
 - Generalized periodic epileptiform discharges
- ROSC >3h from time of ED arrival (Treatment allocation must be within 4h so anything that will prevent this is reason for exclusion)
- Alert and interactive patient with minimal evidence of neurologic injury
- Plan to extubate within 12 hours
- PCAS opinion that patient will die with >95% likelihood. This may be based on:
 - Multiple medical comorbidities
 - Late discovery of DNR or advanced directive
 - Terminal diagnosis (other than OHCA; may have caused OHCA)
 - Clinical judgement based on current exam and data
- Known intracranial hemorrhage or acute cerebral infarction; Head CT is NOT REQUIRED prior to enrollment
- Patient is known to be taking PDE5 inhibitors, sGC stimulator, or has a known diagnosis of Chronic thromboembolic pulmonary hypertension (CTEPH), pulmonary hypertension (PAH), or erectile dysfunction
- Known enrollment in another acute interventional trial

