6.4.3 Parameters to be Monitored

The following progress will be monitored throughout the course of the research to ensure the safety of subjects as well as the integrity and confidentiality of their data.

- An evaluation of the progress of the research study, including subject recruitment and retention, and an assessment of the timeliness and quality of the data.
- A review of collected data (including adverse events, unanticipated problems, and subject withdrawals) to determine whether there is a change to the anticipated benefit-to-risk assessment of study participation and whether the study should continue as originally designed, should be changed, or should be terminated.
- An assessment of external factors or relevant information (eg. pertinent scientific literature reports or therapeutic development, results of related studies) that may have an impact on the safety and study participants or the ethics of the research study.
- A review of study procedures designed to protect the privacy of the research subjects and the confidentiality of their research data.

The severity of adverse changes in physical signs or symptoms will be classified as follows:

- Grade 1 (Mild): asymptomatic or mild symptoms; clinical or diagnostic observation only; intervention not indicated.
- Grade 2 (Moderate): minimal, local or noninvasive intervention indicated; limiting age-appropriate ADL (Activities of Daily Living).
- Grade 3 (Severe): medically significant but not immediately life-threatening; hospitalization or prolongation of hospitalization indicated; disabling; limiting self care ADL.
- Grade 4 (Life-threatening): consequences; urgent intervention indicated.
- Grade 5 (Death): event is a direct cause of death.

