- Other common post-OHCA SAE (Grade 3 unless specified) include pneumonia, cerebral bleeding, stroke, seizures, bleeding requiring transfusion or surgical intervention, rearrest (Grade 5), rib fractures, sternal fractures, internal thoracic or abdominal injuries as well as any other major medical or surgical outcomes will be recorded as noted in the hospital discharge summary.

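### The fixed grades in 6.4.5 contradict the severity scale in 6.4.3: every rearrest is graded as a death, and fatal bleeding is graded as non-fatal

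*Combined protocol and SAP*

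**What the plan says.** Section 6.4.3 (Parameters to be Monitored) sets a five-level severity scale. The top two levels read "Grade 4 (Life-threatening): consequences; urgent intervention indicated" and "Grade 5 (Death): event is a direct cause of death". Which of the two applies depends on what the event led to, not on what kind of event it was.

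Section 6.4.5 (Reportable Adverse Events) then gives a list headed "Expected SAE (with severity grade indicated)", in which grades are attached to event types. Its last item begins "Other common post-OHCA SAE (Grade 3 unless specified) include pneumonia" and, within that item, marks one event differently: "rearrest (Grade 5)". Earlier in the same list, under the events anticipated with therapeutic hypothermia, the bleeding item runs from overt bleeding with a haemoglobin drop through to fatal bleeding. The whole item carries Grade 3.

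Section 2.5.4 (Safety Analysis) states: "All listed safety outcomes will be tabulated and summarized using basic descriptive statistics and tested using small sample exact methods." It does not mention grade.

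**The concern.** A grade fixed by event type cannot agree with a scale defined by outcome when the event can end either way. Rearrest can be survived or not, and so can a major bleed. Under 6.4.5 the grade of a rearrest says that the subject died of it whatever happened, and the grade of a fatal bleed says that the subject did not die of it.

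What is at stake is the accuracy of the safety record. Rearrest is a relevant cardiac safety event in a trial whose hypothesis is reduced heart injury. The DSMB reviews adverse events and, under 6.4.7, is the only body that can stop the study. If it or a later reader is shown adverse events by grade, the Grade 5 row would mix deaths with survived rearrests and leave out deaths from bleeding. It would not match the mortality figures beside it.

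**Working it through.** There is no stated figure to reproduce. The check is a comparison of sections.

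1. **Is the Grade 5 for rearrest deliberate?** The item sets Grade 3 as its default and overrides it for rearrest alone. The text is therefore an explicit assignment. Nothing in it limits the grade to fatal rearrest.

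2. **Does the protocol expect rearrests that are survived?** Yes, by inference from two places. Section 3.3 excludes only patients with "> 1 recurrent arrest prior to enrollment", so someone who has survived one recurrent arrest can be enrolled. That criterion concerns arrests before enrolment, which are not on-study events, but it shows that the protocol regards rearrest as survivable. Section 2.2 lists CPR among the interventions recorded on days 1 to 3, so arrests after enrolment are anticipated, and 6.4.5 itself describes the events in this item as common.

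3. **What happens to a survived rearrest?** By 6.4.3 it cannot be Grade 5, because it caused no death. By 6.4.5 it is Grade 5. Both cannot be followed.

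4. **What happens to a fatal bleed?** By 6.4.3, a bleed that directly causes death is Grade 5. By 6.4.5 it is Grade 3. This is the same conflict in the opposite direction.

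5. **Where is grade used?** Section 2.5.4 tabulates by listed outcome. A serious unanticipated event is defined in 6.4.5 by methaemoglobin above 10%; 6.4.6 adds events found on unblinding to be drug associated. Unblinding (2.3.5), the reporting timeline (6.4.6) and discontinuation (6.4.7) do not refer to grade.

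6. **Where are deaths counted?** Section 2.2 records survival at discharge, day 30 and day 90 as an essential item, and also lists cause of death and date and time of death. In-hospital death in the primary composite does not depend on an adverse event grade.

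7. **Size per event, if a table by grade is made.** With 130 subjects randomised 1:1, each arm has 130 / 2 = 65. If each affected subject has one such event, each survived rearrest adds 1/65 = 1.5 percentage points to that arm's Grade 5 proportion, and each fatal bleed held at Grade 3 removes 1.5 points. The documents give no rate for either event, so the net effect, and even its direction, cannot be derived.

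**The case against.** The strongest reply is that the label does no work. The unit of tabulation in 2.5.4 is the listed outcome, so rearrest would appear as rearrest. No section specifies a table by grade or derives deaths from Grade 5 events, and grade triggers no unblinding, report or stopping decision. The safety monitor sees final outcomes at least every 4 weeks (6.4.4). All of this stands, and it limits the point to the consistency of the safety record.

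A reader might infer that survived rearrests would be presented to the DSMB as deaths and that fatal-event counts by arm would be overstated. The documents do not support that: the DSMB duties in 6.4.2 mention adverse events but set no table format, and mortality has its own data fields. A reader might also infer that fatal and non-fatal rearrest could not be told apart. That goes too far as well. Rearrest, survival, cause of death and time of death are all recorded and can be linked by subject. Cause of death, time of death and CPR are not marked as essential items, so the linkage may be incomplete, but it is possible.

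One could also say that the entry was meant to cover fatal rearrest only. The text does not say so, and on that reading survived rearrest would have no clear place in the list. Either way the wording needs an edit.

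**Conclusion.** The inconsistency is real and can be seen from the text alone. Section 6.4.5 attaches the grade that means death to every rearrest and a non-fatal grade to fatal bleeding, and both contradict 6.4.3. The consequence is conditional: if adverse events are summarised by grade, that summary will disagree with the survival data. The primary composite, the survival endpoints, the sample size and the stated reporting and stopping rules are untouched. The conclusion assumes only that some rearrests are survived or some bleeds are fatal, both of which the protocol's own wording allows for. The number of affected events is unknown. This is a minor point, worth correcting because the correction costs so little.

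**What to change.** In 6.4.5 and on the adverse event form, replace the fixed grades for rearrest and bleeding with grading by the 6.4.3 definitions: Grade 5 only when that event directly causes death, otherwise the grade that those definitions give. Changing rearrest alone would leave the bleeding conflict in place, so both should be edited together. In the safety tabulation under 2.5.4, report fatal and non-fatal rearrest separately by arm.

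The cost is a short text edit and a small addition to the adverse event form and the safety table. It concerns classification and reporting only; patient care, design and the primary analysis do not change.
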